#### *Data Assessments.*

The pre- and then post-contrast US imaging will be evaluated for each patient at all 4 time points in one reading as follows: grayscale, grayscale and PDI (baseline), and grayscale and 3D SHI. While this may introduced some bias from pre- to post-contrast results, we considered this the

more realistic approach to how US contrast may be used in clinical practice. Each case will be read independently by the 2 experienced co-investigators (more than 15 years of expertise in breast imaging) blinded to the contrast-enhanced MRI evaluations, to allow repeatability to be assessed. All US studies will be rated on a quasi-continuous scale from 0 to 100 ranging from “no change relative to pre-therapy” over “indeterminate” to “definite changes seen.” Using a quasi-continuous 100-point rating scale has an intuitive probabilistic interpretation and is known to improve the assessment of the capabilities of the imaging modes studied.

Moreover, the 3D SHAPE results (i.e., IFP estimates) will be compared to lesion size, tumor response, DFS and overall survival. Results will also be compared to MRI enhancement kinetics and imaging measurements of lesion size obtained before and after completion of the chemotherapy. Once surgery has been performed the following variables estrogen, progesterone and HER2 receptor presence or absences; presence or absence of hemorrhagic, necrotic, or other component of the lesion (and their location if present); histological margins; lesion size; TNM staging; histological lesion type; presence or absence of vascular invasion; histological and cytological grade; presence or absence of metastases; node staging; and percentage of the lesion that was invasive or *in situ* will be collected as part of the patient’s clinical care and correlated with the imaging results. Finally, the ability of 3D SHI to image angiogenesis (specifically fractional tumor vascularity) will be compared to specimens stained for an immunohistochemical predictor of angiogenesis, specifically a monoclonal antibody against the PECAM endothelial cell marker (anti-CD31; Dako Corporation, Carpinteria, CA). The PI has developed the necessary software for quantitative analysis of contrast enhanced US images and specimens

stained with CD31 using a histomorphometry system based on an SMZ-10A microscope (Nikon, Melville, NY) and ImagePro Plus software.

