*Statistical Analysis.* Our statistical analysis will address the primary objective of this study by answering two major questions:

1. Can *in vivo* 3D SHAPE monitor the effect of neoadjuvant chemotherapy on breast cancer IFP?
2. Can *in vivo* 3D SHI monitor the effect of neoadjuvant chemotherapy (i.e., responders/non-responders) on breast cancer?

The findings of SHI/SHAPE will be correlated to vascular morphology (i.e., tumor angiogenesis ascertained with CD31) and other pathological findings; including size, vascularity, presence or absence of receptors. For the pre and post-contrast enhanced comparisons, dichotomous parameters (e.g., responder/non-responder) and ranked data (less, iso, or more intense) will be analyzed with the McNemar test which measures significance of changes in related samples (pairwise comparisons) for each time point. For variables in which accurate numerical measurement is possible (e.g., IFP and vascularity), the techniques will be compared using repeated measures logistical regression and ANOVA.

To answer statistical question 2, the ability of the imaging tests to distinguish responders from non-responders will be compared using ROC analysis, while the incremental validity of combining imaging assessments will be analyzed using logistic regression and ROC analyses. The tests are fundamental grayscale US imaging, PDI, 3D SHI and contrast

enhanced MRI, while patient outcomes and pathology will provide the reference standards. A power analysis was performed using PASS 12 (NCSS, East Kaysville, UT) to estimate the number of cases required to produce clinically acceptable results. A sample size of 20 responders and 20 non-responders (i.e., approximately halfway between 20 and 50 subjects) achieve 80% power to detect a difference of 0.174 between a diagnostic test with an area under the ROC curve ( $A_z$ ) of 0.800 (the null hypothesis) and an actual  $A_z$  of 0.974 using a one sample, two-sided z-test with a significance level of 0.05. The ratio of the standard deviation of the responses in the two groups was assumed to be 1.00. All analyses will be performed with Stata 12.0 (Stata Corp., College Station, TX).

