#### **7.2.2 Analysis of Results**

For the pre and post-contrast enhanced comparisons, dichotomous parameters (e.g., responder/non-responder) and ranked data (less, iso, or more intense) will be analyzed with the McNemar test which

measures significance of changes in related samples (pairwise comparisons). For variables in which accurate numerical measurement is possible (e.g., IFP and vascularity), the techniques will be compared using logistical regression and an ANOVA.

The ability of the imaging tests to distinguish responders from non-responders will be compared using ROC analysis, while the incremental validity of imaging assessments will be analyzed using logistic regression and ROC analyses. The tests are fundamental grayscale US imaging, PDI, 3D SHI and contrast enhanced MRI, while patient outcomes and pathology will provide the reference standards. All studies will be rated on a quasi-continuous scale from 0 to 100, since this has an intuitive probabilistic interpretation and improves the assessment of the characterization capabilities of the imaging modalities compared to using a coarser 6-point scale. Logistical regression techniques will be used to combine the 3 US imaging modes and MRI as well as to incorporate the quantitative parameters (i.e., SHAPE IFP estimates) into the US evaluation before repeating the ROC analysis. This will allow all possible combinations to be compared to one another (e.g., MRI versus all the US modes combined or MRI and grayscale US versus MRI and grayscale US and SHI, etc.). Differences between ROC curves will be tested by computing Mann-Whitney statistics.

All histopathological variables will be compared to imaging judgments of vascularity for the different modalities. When both sets of variables are nominal, chi-square tests will be conducted. When both types of variables are ordinal or continuous, correlations will be calculated. When one type of variable is nominal and one continuous non-parametric rank order tests such as Mann-Whitney U-tests or Kruskal-Wallis tests will be performed. Inter-observer variability will also be determined by calculating the intraclass correlation coefficient.

Comparisons of subject outcomes (i.e., responders vs. non-responders) established by monitoring the treatment with the different imaging modalities will be conducted with Cox Survival analysis (against

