the pathological reference standard). For the US techniques where data from multiple time points are available, this analysis will be repeated for each time point. All of the statistical analyses proposed for the human clinical trial will be repeated split by racial and ethnic groups to determine if clinically important race/ethnicity differences exist in the ability of 3D SHI/SHAPE to monitor breast cancer treatment.

Finally, the vascularity measures obtained from the CD31 stained breast tumor specimens will be compared to the fractional tumor neovascularity data to determine if any correlation exists (in baseline PDI or contrast enhanced mode). The existence of a linear relationship between US and pathologic data will be assessed using single variable linear regression techniques and reverse stepwise multiple linear regression analysis.

All analyses and computations will be performed using Stata 12.0 (Stata Corporation, College Station, TX), while the study database will be designed and implemented in Filemaker Pro 10.0 (Filemaker Inc, Santa Clara, CA). This database will contain all patient information (except names and other identifiers) and the results of the various US imaging modes as well as the pathology results.

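### No decisive ROC analysis is named for whether 3D SHI monitors response: comparator, scan, reader rule and multiplicity control are all left open

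*Combined protocol and SAP*

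**What the plan says.** Section 4, Statistical Analysis, states: "Our statistical analysis will address the primary objective of this study by answering two major questions". Question 1 concerns SHAPE and interstitial fluid pressure; question 2 concerns 3D SHI and response. Neither is given priority.

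For question 2, section 4 and section 7.2.2 both plan ROC comparisons of four tests: grayscale US, PDI, 3D SHI and contrast-enhanced MRI. Section 7.2.2 adds logistic models that combine the tests and bring in the SHAPE estimates, and then says: "This will allow all possible combinations to be compared to one another". Differences between curves are tested with Mann-Whitney statistics. No significance level is given there.

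The only stated error rate is in the power statement (Synopsis and section 4). It covers "A sample size of 20 responders and 20 non-responders" and an area of 0.974 against a fixed null of 0.800, "using a one sample, two-sided z-test with a significance level of 0.05". It does not say which imaging test, scan or reader it concerns, and section 7.2.2 does not list a one-sample test.

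On readers, section 4, Data Assessments, says: "Each case will be read independently by the 2 experienced co-investigators". The stated purpose is repeatability. No rule says how two sets of ratings enter one ROC curve. US is done at four time points; MRI is done before and after chemotherapy only.

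Section 7.2.2 also plans tests of pathology against imaging ("All histopathological variables will be compared to imaging judgments of vascularity for the different modalities") and a repeat of all analyses by race and ethnicity.

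**The concern.** The candidate ROC contrasts can disagree. SHI could do better than PDI at an early scan and worse than MRI after chemotherapy, or do better for one reader only. Nothing in the plan says which result answers question 2, so the choice can be made after the results are seen. A 5% error rate does not describe a claim chosen in that way.

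The power statement does not fill the gap. The test that has a stated error rate is not among the planned analyses, and the planned paired comparisons have no stated error rate.

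At stake is the main conclusion of the trial. Section 7.2.1 hypothesises that the subharmonic information will improve response monitoring, and under the plan any one of many contrasts could be offered as support for it.

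**Working it through.** **1. The plan's own figure.** Inputs from section 4: 20 + 20 subjects, null area 0.800, true area 0.974, SD ratio 1.00, two-sided 0.05. Power = Φ[(0.174 − 1.96·SE₀)/SE₁]. The binormal variance gives SE₀ = 0.0775 and SE₁ = 0.0264:

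(0.174 − 1.96 × 0.0775)/0.0264 = 0.0221/0.0264 = 0.84, and Φ(0.84) ≈ 80%.

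The stated 80% is reproduced, for one one-sample test.

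**2. Size of the comparison set in section 7.2.2.** Non-empty sets of four tests: 2⁴ − 1 = 15. Pairs: 15 × 14/2 = 105. With SHAPE as a fifth component: 2⁵ − 1 = 31 sets and 31 × 30/2 = 465 pairs.

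**3. SHI against single tests only.** Ratings express change from pre-therapy, so three follow-up scans are usable, and MRI is available at the last one only.
- One scan (the last), one reader: SHI v grayscale, PDI and MRI = 3 contrasts.
- Three scans, one reader: 2 comparators × 3 scans + 1 MRI contrast = 7.
- The same for two readers separately: 14.

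**4. False-positive rates.** If the tests were independent, the chance of at least one false positive would be 1 − 0.95^k. The real contrasts share subjects and share SHI, so paired nonparametric (DeLong) tests were simulated: 3,000 trials per setting, 20 + 20 subjects, every test at area 0.80, each contrast at two-sided 0.05. Assumed correlations were 0.3 to 0.7 between modalities, 0.3 to 0.9 between scans and 0.5 to 0.95 between readers. None of these is given in the documents.

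| SHI contrasts | If independent | Simulated, either direction | Simulated, SHI favoured |
|---|---|---|---|
| 3 (last scan, one reader) | 14.3% | 10–14% | 5–7% |
| 6 (last scan, two readers) | 26.5% | 15–23% | 7–11% |
| 7 (three scans, one reader) | 30.2% | 17–26% | 8–13% |
| 14 (three scans, two readers) | 51.2% | 23–44% | 11–24% |

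The single-direction column uses a subset of the same correlation settings; its nominal rate for one test is 2.5%. The average rejection rate per test was 4% to 5%, so the excess comes from the number of contrasts and not from a faulty test.

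**5. What is not counted.** The table leaves out the combination models, the SHAPE question, the race and ethnicity splits and the pathology tests. It therefore does not measure the full set of combinations that section 7.2.2 asks for.

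**The case against.** The strongest reply is that much of the multiplicity is inferred. A reader might take the plan to prescribe ROC tests at every scan and for each reader at an unadjusted 0.05, and so to carry an error rate near 40%. The documents do not say that.
- The sentence "this analysis will be repeated for each time point" concerns the Cox analysis. The matching words in section 4 concern the McNemar test. Neither mentions ROC.
- Two readers are used for repeatability, which section 7.2.2 assesses by intraclass correlation. Reader-specific ROC tests are not planned.
- The 0.05 level appears only in the power statement.

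All of this stands. The 14-contrast figure is what the open choices permit, not what the plan schedules. The harm described is also a false claim for SHI, which is about half as likely as a false difference in either direction.

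It can also be said that a single-site, first-in-humans study of 20 to 50 women need not control a familywise rate strictly. That is fair, and an exploratory label would be a proper answer, but the plan does not apply one.

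What the objection does not remove is the narrowest case. Three SHI contrasts at one scan with one reader need no assumption of repeated scans or readers and still give 10% to 14% if each is tested at 0.05. The intention to compare all combinations is explicit. Silence on scan and reader rule is part of the defect, because it leaves those choices open until results are known.

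**Conclusion.** The concern holds in this form: question 2 has no decisive ROC analysis. The plan names no primary comparator, scan or reader rule, states no multiplicity control or exploratory label, and powers a test that the analysis section does not list.

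If each comparison is tested at two-sided 0.05, the chance of a false SHI difference exceeded 5% in every setting tried. It ranged from about 10% for the narrowest reading to about 44% for the widest. The figure depends on how many contrasts are counted and on assumed correlations, so no single rate should be quoted as a property of the plan. This should be corrected before any confirmatory claim is made for SHI.

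**What to change.** In section 4, Statistical Analysis, and section 7.2.2:

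1. Name one primary SHI analysis for question 2: one comparator (or the powered one-sample test against 0.800), one scan, and one rule for combining the two readers, tested once at two-sided 0.05. The choice is the sponsor's but should fit the objective, which names MRI and pathology. A comparison with MRI on change from pre-therapy is possible only after chemotherapy.
2. State how questions 1 and 2 share the error rate, for example by Holm, or state that they are separate questions with no joint claim.
3. Label all other ROC and combination comparisons, reader-specific results, race and ethnicity splits and pathology tests as exploratory, reported as estimates with 95% confidence intervals.

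A single pre-specified test brings the false-positive chance back to 5% (4% to 5% simulated). Keeping all 14 SHI contrasts confirmatory would instead need about 0.05/14 = 0.0036 each by Bonferroni.

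The cost is wording, with no added patients or scans, but contrasts outside the primary analysis can no longer support a confirmatory claim. If a paired contrast is chosen, the stated 80% power does not carry over. With 20 + 20 subjects and an assumed correlation of 0.3 to 0.7 between tests, simulated power is about 78% to 91% for 0.974 v 0.800, but only about 24% to 40% for 0.90 v 0.80. The plan should give the power of whichever analysis it names.

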### *Patient Enrollment*

At TJU, [name] (the medical oncologist on this project) and her colleagues treat more than 500 women with breast cancer each year out of which 1-2 women/week will be treated with neoadjuvant chemotherapy. We expect to enroll between 20 and 50 subjects undergoing neoadjuvant chemotherapy (i.e., 10 – 25 women/year) in this *first-in-humans* project who will be studied with contrast US (SHI and SHAPE) before as well as with around 10 % and 60% of the neoadjuvant chemotherapy treatment delivered and after completion of the last chemotherapy treatment. Thus, a total of some 144 contrast studies will be performed in this project (range: 80 – 200). The patients studied in this project will be women over the age of 21, who will receive an MRI as part of their standard of care (before and after completion of the chemotherapy). The MRI results together with pathology findings will be compared to the 3D SHI and SHAPE studies as a means for treatment monitoring.

Given that these women have been diagnosed with breast cancer, they are usually very motivated to participate in research studies that include additional monitoring and, therefore, we do not expect recruitment to be an issue. The patient population of this project will reflect the population demographics found at major American urban academic health centers. The overall hospital demographics for TJU include 60 % Caucasian, 16 % African American, 13 % Hispanic, 5 % Asian, 1 % Other, and 5 % unknown patients. Breast cancer in males accounts for only about 1% of cases at TJU and, thus, will not be included in the patient population.

The inclusion criteria for this trial are as follows:

- Females
- Be diagnosed with T1 or greater LABC, any N and M0.

- Be scheduled for neoadjuvant chemotherapy
- Be at least 21 years of age.
- Be medically stable.
- If a female of child-bearing potential, must have a negative pregnancy test.
- Have signed Informed Consent to participate in the study.

The exclusion criteria are:

- Males
- Females who are pregnant or nursing.
- Patients with other primary cancers requiring systemic treatment.
- Patients with any metastatic disease.
- Patients undergoing neoadjuvant endocrine therapy.
- Patients with known hypersensitivity or allergy to any component of Definity.
- Patients with cardiac shunts or congenital heart defects.
- Patients with unstable cardiopulmonary conditions or respiratory distress syndrome.

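### The plan reruns every analysis within racial and ethnic groups to find differences between them, but plans no between-group comparison, and the minority groups are too small to support the responder analyses

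*Combined protocol and SAP*

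**What the plan says.** Section 7.2.2 (Analysis of Results) commits to a rule: "All of the statistical analyses proposed for the human clinical trial will be repeated split by racial and ethnic groups". It gives the purpose in the same sentence: "to determine if clinically important race/ethnicity differences exist in the ability of 3D SHI/SHAPE to monitor breast cancer treatment". The analyses to be repeated include McNemar tests, ANOVA, ROC comparisons, logistic models combining imaging modes, correlations and rank tests against histology, Cox models, and linear and stepwise regression.

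On numbers, section 4 (Patient Enrollment) says "We expect to enroll between 20 and 50 subjects undergoing neoadjuvant chemotherapy" and gives the hospital mix as "60 % Caucasian, 16 % African American, 13 % Hispanic, 5 % Asian, 1 % Other, and 5 % unknown patients". It expects that "The patient population of this project will reflect the population demographics found at major American urban academic health centers".

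The only power calculation (Synopsis, and Statistical Analysis in section 4) is for the whole sample: "A sample size of 20 responders and 20 non-responders" for "80% power to detect a difference of 0.174 between a diagnostic test with an area under the ROC curve" of 0.800 and an actual 0.974, two-sided at 0.05. The documents give no subgroup sizes, interaction term, between-group test, pooling of small groups or multiplicity control, and they do not label the analysis exploratory.

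**The concern.** The question is comparative: does the imaging perform differently in different groups? The method is not. A result in one group and another result in a second group, each tested against its own null, do not show that the two differ. With groups of very unequal size, different p-values are expected even when performance is identical. The section does not say how the separate results would be turned into a conclusion, so that step is left to whoever reads the tables.

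At stake is a statement, positive or negative, about whether a new imaging method works equally well across racial and ethnic groups. Under this plan such a statement would rest on a handful of patients per minority group and on no direct comparison.

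**Working it through.** **Inputs.** Enrolment 20 to 50 and the hospital mix (section 4, Patient Enrollment); 20 responders and 20 non-responders, areas 0.800 and 0.974, two-sided 0.05, SD ratio 1.00 (section 4, Statistical Analysis). Assumptions: the trial mix equals the hospital mix, each group splits evenly into responders and non-responders, and there is no dropout.

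**1. The plan's own power figure.** Binormal variance of an estimated area A: V(A) = 0.0099 · exp(−a²/2) · [(5a² + 8) + (a² + 8)/k], with a = 1.414 · z(A) and k = 1.
- A = 0.800: a = 1.190, V = 0.1195.
- A = 0.974: a = 2.748, V = 0.01392.
- With 20 per class: √(0.1195/20) = 0.0773 and √(0.01392/20) = 0.0264.
- Power = Φ[(0.174 − 1.96 × 0.0773)/0.0264] = 80.3%.

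This agrees with the stated 80%. The Hanley-McNeil variance gives 90.8%, so the binormal form is used below.

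**2. Expected group sizes** (N × share)

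| Group | N = 20 | N = 40 | N = 50 |
|---|---|---|---|
| Caucasian | 12 | 24 | 30 |
| African American | 3.2 | 6.4 | 8.0 |
| Hispanic | 2.6 | 5.2 | 6.5 |
| Asian | 1.0 | 2.0 | 2.5 |
| Other | 0.2 | 0.4 | 0.5 |
| Unknown | 1.0 | 2.0 | 2.5 |

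**3. Exact rank test, responders v non-responders.** The smallest two-sided p is 2/C(n₁ + n₀, n₁):
- 3 v 3: 2/20 = 0.10.
- 3 v 2: 2/10 = 0.20.
- 1 v 1: 1.0.
- 3 v 4: 2/35 = 0.057.
- 4 v 4: 2/70 = 0.029, so 0.05 comes within reach at eight patients.

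**4. The AUC z-test within a group.** To show an area above 0.800, the estimate must exceed 0.800 + 1.96 · √(0.1195/n), with n per class.

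| Group | n per class | Limit | Power at 0.974 |
|---|---|---|---|
| African American, N = 40 | 3.2 | 1.18 | 0.1% |
| African American, N = 50 | 4 | 1.14 | 0.3% |
| Caucasian, N = 20 | 6 | 1.08 | 1.7% |
| Caucasian, N = 40 | 12 | 0.996 | 26% |
| Caucasian, N = 50 | 15 | 0.975 | 49% |

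A limit above 1 cannot be met; the small powers beside such limits come only from the normal approximation. The lower tail stays open (0.800 − 1.96 × 0.193 = 0.42), but that would show a worse test, not a working one. As a guide to precision, an area of 0.80 at 3 v 3 has a Hanley-McNeil standard error of 0.199, so the approximate 95% interval is 0.80 ± 0.39, from 0.41 to beyond 1.

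**5. Models.** Section 7.2.2 combines three ultrasound modes, MRI and the SHAPE pressure estimate in logistic regression: five predictors plus an intercept, six parameters. That matches the whole expected African American group at N = 40 and exceeds the Hispanic and Asian groups. In a group of two, the chance that both fall in one response class, leaving no ROC curve, is 2 × 0.5² = 50%.

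**6. A direct comparison of two groups at N = 40.** Caucasian area 0.974 (12 per class) v African American 0.800 (3.2 per class): SE = √(0.01392/12 + 0.1195/3.2) = 0.196. Power = Φ(0.174/0.196 − 1.96) = 14%. The same sum gives 17% at N = 50 and 9% at N = 20. With the Caucasian area at 0.974, no lower African American area down to about 0.5 gives 80% power at N = 40. With the areas exchanged, SE = √(0.1195/12 + 0.01392/3.2) = 0.120 and power is about 31%. These are large-sample formulas at very small n and show order of magnitude only.

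**7. Planned tests that can reach 0.05 in small groups.** Exact McNemar at n = 6: 2 × 0.5⁶ = 0.031, if all six pairs change in the same direction. Exact Spearman: 2/5! = 0.017 at n = 5 and 2/6! = 0.003 at n = 6, with perfect ordering. Pearson needs |r| of at least 0.878 at n = 5 and 0.811 at n = 6. The rank-sum test by normal approximation gives 0.0495 at 3 v 3 with complete separation.

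**The case against.** A reader might infer three stronger things that the documents do not support.

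- *That all groups will be tiny.* The Caucasian group is expected to hold about 24 (12 to 30 over the enrolment range), and the African American group reaches 8 at N = 50. Chance matters too: at N = 40 the probability of eight or more African American patients is about 30%.
- *That no data could reach significance, or no analysis could be run.* Step 7 refutes the first. The plan does not require exact p-values, and an empirical ROC curve can be drawn at 3 v 3. The multivariable logistic, Cox and stepwise models are the ones likely to fail.
- *That the result will be significance in Caucasian patients and nowhere else.* For the AUC test, Caucasian power is only 26% at N = 40, so non-significance everywhere is more likely. Nor does section 7.2.2 say that groups will be compared by significance; it leaves the rule unstated.

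It can also be said that this is one sentence in a first-in-humans study, outside the specific aims and the two stated statistical questions, and that a formal interaction would itself have low power. Both are true. They argue for a modest remedy. They do not rescue the sentence, which states a purpose of reaching a conclusion and supplies no comparison from which to reach it.

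**Conclusion.** The concern holds in this form: the plan sets out to determine whether differences by race or ethnicity exist, plans no comparison between groups, and relies on separate analyses that do not test a difference. The absence of a comparison is a defect at any sample size.

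At N = 40 the minority groups of about 2 to 6 cannot give an exact rank-test p below 0.05 for response and cannot show an area above 0.800 on the z-test. They are unlikely to support the multivariable models. Where other planned tests can reach 0.05, they need extreme data from five or six patients, which would be poor ground for a conclusion. The figures rest on the hospital mix applying to the trial, an even responder split within groups and no dropout. The mix is the weakest of these, since it describes the hospital and not women receiving neoadjuvant chemotherapy. The change should be made, but the study's main analyses are not affected.

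**What to change.** Replace the sentence in section 7.2.2 with:

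> Race/ethnicity differences will be explored in the pooled sample by an imaging-by-group interaction (Caucasian v all other known groups) in the logistic model of response on the 3D SHI rating, and likewise for the SHAPE IFP estimate, reported as an estimate with 95% CI and labelled exploratory. Results by individual group will be descriptive only (counts, estimates and CIs where estimable), without p-values, and no conclusion about the presence or absence of a race/ethnicity difference will be drawn from separate within-group significance.

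The time point of the rating and of the pressure estimate should be named in the same sentence.

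The cost is wording only; no patients, visits or data are added. Less is claimed for individual groups, and pooling hides differences among the smaller ones. The estimate will still be imprecise. The other known groups make up 16 + 13 + 5 + 1 = 35%, or 14 patients at N = 40 (7 per class). For areas of 0.974 v 0.800 the SE is √(0.01392/12 + 0.1195/7) = 0.135, and power is Φ(0.174/0.135 − 1.96), about 25%. That is why the replacement asks for an interval and an exploratory label and not for a test.

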## **3. Specific Aims for the Human Clinical Trial.**

- 1) To evaluate the ability of 3D SHI and SHAPE to track changes in LABC angiogenesis and IFP, respectively, by studying women undergoing neoadjuvant chemotherapy before as well as with around 10% and 60% of the neoadjuvant chemotherapy treatment delivered and after

completion of the neoadjuvant chemotherapy treatment and comparing results to MRI and pathology.

- 2) Finally, as a secondary aim, to compare the 3D SHI depiction of breast cancer angiogenesis in humans to CD31, an immunohistochemical predictor of angiogenesis.

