## 6.7 End-of-Treatment and End-of-Trial Evaluations

### 6.7.1 Discontinuation of Subjects

Subjects will be free to discontinue trial participation at any time. The investigator will also discontinue any subject from the trial if, in the investigator's opinion, it is not safe for the subject to continue. The date the subject is withdrawn from a treatment and/or from the trial and the reason for discontinuation will be recorded on the CRF.

Trial participation will be considered completed if the subject has met all of the trial requirements that is to participate in 4 US contrast studies during the duration of their clinical cancer treatment.

If a subject's participation in the trial is interrupted for any reason (e.g., because of an AE or if the subject is lost to follow-up) and the subject has met the criteria described above for completing the trial, the subject's trial participation will be considered completed. If a subject's trial participation is interrupted

for any reason by the subject's or investigator's choice and the subject has not met all of the criteria listed above, then the subject will be considered a discontinued subject.

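### The CD31 aim has two unranked regression methods, one of them reverse stepwise with no limit on candidates, so its p-values and R-squared can be optimistic by an amount the plan leaves open

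*Combined protocol and SAP*

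**What the plan says.** Section 3 sets the secondary aim: "to compare the 3D SHI depiction of breast cancer angiogenesis in humans to CD31, an immunohistochemical predictor of angiogenesis". No other secondary aim is listed.

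The last part of Section 7.2.2 gives the analysis. CD31 vascularity is compared with fractional tumor neovascularity, "in baseline PDI or contrast enhanced mode", to see whether they correlate. Linearity is then assessed by regression on one variable at a time and by "reverse stepwise multiple linear regression analysis".

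The plan does not give:
- the candidate predictors or their number;
- which of the four ultrasound time points is used;
- the removal threshold;
- any validation, shrinkage or multiplicity adjustment;
- the number of patients expected to have an evaluable CD31 specimen;
- a rule for which of the two regressions answers the aim.

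**The concern.** Backward elimination uses the outcome to choose its predictors. The p-values, intervals and R-squared of the final model are then computed as though that model had been fixed beforehand, so they look better than they should. The size of the error grows with the number of candidates, and the plan sets no limit on that number.

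At stake is how the aim 2 result can be read. The stepwise model could show a nominally significant link between ultrasound and CD31, with a respectable R-squared, that comes from selection alone. Because the two methods are unranked, nothing says which result counts if the single-variable regression shows no relation and the stepwise model does.

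**Working it through.** **The plan's own figure.** The only sample-size figure is 80% power for the ROC comparison (Section 4, Statistical Analysis), from a "one sample, two-sided z-test with a significance level of 0.05". It reproduces with the Obuchowski rating-data variance for equal groups, V = 0.0099·exp(−a²/2)·[(5a²+8)+(a²+8)], where a = 1.414·Φ⁻¹(Az). With 20 per group, SE = √(V/20), which is 0.0773 at Az 0.800 and 0.0264 at 0.974. Power = Φ((0.174 − 1.96×0.0773)/0.0264) = 0.80. This figure does not bear on the CD31 regression, for which no power or error rate is stated.

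**Inputs from the documents.**
- Number of patients: the enrollment text gives 144 contrast studies (range 80 to 200), and completing the trial means to "participate in 4 US contrast studies". So 144/4 = 36, with range 80/4 = 20 to 200/4 = 50. The power text has "A sample size of 20 responders and 20 non-responders", which is 40.
- Predictors named for CD31: fractional vascularity in two modes, PDI and contrast-enhanced.

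**Assumptions.**
- Number of candidates k: 2 (the modes named), 4, 8 (two modes × four time points) and 12. Nothing in the documents points to 12; it shows the trend.
- Removal level: 0.05 to 0.10.

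**Check.** Simulate a normal outcome and k independent normal predictors unrelated to it. Fit all k, drop the one with the largest p-value, and refit until every remaining p-value is below the removal level. Count the data sets whose final model holds at least one predictor at p<0.05. For comparison, 1 − 0.95^k is the chance that at least one of k independent tests reaches p<0.05 with no stepwise selection.

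| k | 1 − 0.95^k | Final model has a p<0.05 (removal 0.05–0.10) | Anything kept at all (removal 0.10) |
|---|---|---|---|
| 2 | 9.8% | 10–11% | 19–20% |
| 4 | 18.5% | 20–22% | 34–37% |
| 8 | 33.7% | 35–41% | 59–61% |
| 12 | 46.0% | 48–57% | 75–79% |

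At removal level 0.05 the two ways of counting coincide. A separate run of 4,000 data sets per setting gave 10–11%, 18–20%, 35–39% and 50–53% for the four rows, so runs agree to about 2 points. That run, and the last column, also cover predictors correlated at 0.5.

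**Share due to stepwise selection.** Subtracting the second column from the third gives 20 − 18.5 = 1.5 to 22 − 18.5 = 3.5 points with 4 candidates, 35 − 33.7 = 1.3 to 41 − 33.7 = 7.3 with 8, and 48 − 46 = 2 to 57 − 46 = 11 with 12. The small differences are within simulation error. The rest is multiplicity from having several candidates.

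**Sample size.** With 8 candidates and removal at 0.05, the rate is 38% at n = 20 and 36% at n = 50.

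**R-squared.** When something is kept, mean R-squared is about 0.12–0.22, against a truth of 0. Part of this is the significance filter alone: one predictor just reaching p = 0.05 has R² = t²/(t²+df), which is 4.13/38.13 = 0.11 at n = 36 and 4.10/42.10 = 0.10 at n = 40.

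**The case against.** The case on the other side is substantial.

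- **The rates are conditional.** A reader might infer that the plan as written yields spurious predictors in 20% to 58% of data sets. The documents do not support that, because they state neither the number of candidates nor the removal level. The two modes they name give about 10%.
- **Stepwise is not the sole method.** A reader might take it to be the only method for aim 2. Single-variable regression is also planned and is listed first. The fair complaint is that the two are unranked.
- **A long candidate list is not stated.** A reader might assume that the many pathology variables enter the stepwise model. Section 7.2.2 assigns histopathological variables to chi-square tests, correlations and rank tests, and nothing says they also enter here. Equally, nothing says what may enter.
- **Small numbers are not the cause.** The rate hardly changes between 20 and 50 patients.
- **Much of the excess is multiplicity.** A fixed two-predictor model also gives at least one p<0.05 in about 10% of null data sets. Removing stepwise without naming one predictor and one time point would gain little.
- **Context.** This is a secondary aim of a first-in-humans study, with no type I error control claimed. The plan is also silent on how the stepwise results would be reported.

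All of this stands, and it limits both the size and the severity. It does not remove the gap: a selection procedure is planned with open inputs and no correction, and the plan does not say that the simpler regression takes precedence.

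**Conclusion.** The concern holds as a minor one. The false-positive rate for the CD31 aim is not fixed by the plan. It is about twice the nominal 5% if only the two named modes compete, and about 35–41% if both modes at all four time points are entered. These figures assume 36 to 40 patients, no true relation, independent normal predictors, removal at 0.05 to 0.10, and a count of final models with any p<0.05. They are rates per data set, not per predictor. Most of the excess comes from the number of candidates. Stepwise selection adds to it as that number grows, and it inflates the reported R-squared. One pre-specified single-variable regression would hold the rate at 5%.

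**What to change.** In Section 7.2.2:

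1. Delete the reverse stepwise step.
2. State that aim 2 is answered by one analysis only: the single-variable regression of CD31 vascularity on 3D SHI fractional vascularity at one pre-specified time point, reported as a slope with 95% CI. The study after completion of chemotherapy is one candidate, being closest to surgery. This presumes that the stained tissue is the surgical specimen, which the plan should state.
3. Add one fixed model with SHI and PDI vascularity at the same time point, labelled supportive, with slopes, 95% CIs and a bootstrap-corrected R-squared. It should not serve as a second route to a positive finding.
4. If stepwise is kept, list its candidates, time points and removal rule, label it exploratory, and bootstrap the whole selection process.

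The cost is a change of SAP wording and somewhat less analysis work. The drawback is a less flexible model, which could miss a relation visible only at another time point or through several variables together.
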